2.2. Study Objectives

Primary objective:

- To assess the safety and tolerability of long-term tofacitinib therapy in subjects with UC.

Secondary objectives:

- To evaluate the efficacy of long-term tofacitinib therapy in subjects with UC.
- To evaluate the effect of long-term tofacitinib therapy on quality-of-life in subjects with UC.

3. INTERIM ANALYSES, FINAL ANALYSES AND UNBLINDING

This is an open-label study. Assignment to tofacitinib will be open to the investigators, patients and the Pfizer study team. There will be no need for unblinding. Knowledge of open-label treatment assignment will not unblind the treatment assignment in the previous double-blinded studies (A3921094, A3921095, or A3921096).

Interim analyses may be performed for study monitoring for internal decision making, application for approval or due to regulatory requests. An independent Data Safety Monitoring Board (DSMB), a group of experts external to Pfizer, will review accumulating safety data from this study on an ongoing basis. Review of efficacy data may occur as part of any risk-benefit assessment deemed the responsibility of this committee. Based on these reviews, the DSMB will have the capacity to make recommendations to Pfizer that might impact the future conduct of the trial. The DSMB will have access to treatment information during the clinical trial. The management and process of this committee will be in accordance with Pfizer's Standard Operating Procedures and will be documented in the DSMB Charter. The DSMB members will all be individuals who are independent of Pfizer.

The final analysis will be performed after the official release of the database.

4. HYPOTHESES AND DECISION RULES**4.1. Statistical Hypotheses**

No formal hypotheses are to be tested.

4.2. Statistical decision rules**4.2.1. Sample Size Rationale**

Approximately 900 subjects are expected to become eligible for the study. Approximately 460 subjects are expected to enroll from the maintenance Study A3921096 assuming a 78% rollover rate from the maintenance study. Approximately 440 subjects are expected to enroll from the induction Study A3921094 or A3921095 assuming that 38% of subjects enrolled in those studies will not achieve clinical response and will not have improving endoscopic subscores after completing induction Study A3921094 or A3921095.

5. ANALYSIS SETS

5.1. Full Analysis Set

The Full Analysis Set (FAS) is defined as all subjects who receive at least 1 dose of study medication in this study.

5.2. Safety Analysis Set

The FAS and the Safety Analysis Set (SAS) are the same.

5.3. Other Analysis Sets

The following subpopulations that are subsets of the FAS population will be used to summarize the efficacy data:

- **Maintenance remission subpopulation:** Subjects that completed the maintenance Study A3921096 in remission. Remission is defined by a total Mayo score ≤ 2 with no individual subscore >1 , and rectal bleeding subscore of 0.
- **Maintenance treatment failure subpopulation:** Subjects that were treatment failures or dropped out due to lack of efficacy from the maintenance Study A3921096 and received tofacitinib 10 mg BID or placebo from induction Study A3921094 or A3921095. Treatment failure was defined by an increase in Mayo score of at least 3 points from the baseline value of Study A3921096, accompanied by an increase in rectal bleeding subscore by at least 1 point, and an increase of endoscopic subscore of at least 1 point yielding an absolute endoscopic subscore of ≥ 2 . In the scenario where the endoscopic subscore is a '3', and the maintenance baseline endoscopic subscore is already a '3' (maximum value), then an increase by at least 1 point will not be needed in order to meet treatment failure. Subjects that completed the maintenance Study A3921096 and fulfilled the definition of treatment failure are included in this subpopulation.
- **Other maintenance completers subpopulation:** All other completed subjects from maintenance Study A3921096, that is, those subjects who were neither in remission nor fulfilled the definition of treatment failure.
- **Induction Non-responder subpopulation:** Subjects who were enrolled from induction Study A3921094 or A3921095 directly but did not achieve clinical response and received tofacitinib 10 mg BID or placebo in the induction studies.

Please notice that some subjects may not be included in any of the subpopulations, such as those in maintenance treatment failure but received tofacitinib 15 mg BID in the induction studies, or those who were enrolled from induction studies directly (in error) but were in clinical response. A listing of subjects that do not meet any of the subpopulation categories will be generated. Central read endoscopic subscore was used in defining these subpopulations.

The analysis described in this SAP may be repeated on the specific country and/or region subpopulation sets in order to meet country-specific regulatory requirements. The subpopulation sets will be the subjects in analysis sets defined in this section who have enrolled from sites in the specific country and/or region.

5.4. Treatment Misallocations

If a subject was enrolled into the study but did not receive any study drug then the subject will be excluded from all the analyses.

5.5. Protocol Deviations

A full list of protocol deviations for the study report will be compiled prior to database closure including protocol deviations related to COVID-19. Per-protocol analysis set is not defined. All analyses will be performed for FAS population and its subpopulations.

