1. AMENDMENTS FROM PREVIOUS VERSION(S)

This document is Version 3 of the statistical analysis plan (SAP) for Protocol A3921139 based on protocol Amendment 11. Although this study used a Data Monitoring Committee (DMC), no changes were based on any result from DMC review.

Major changes from Version 2 to Version 3 include:

- Section 2 was updated based on the protocol Amendments 9, 10 and 11.
- Section 5.5 was updated to mention protocol deviations related to COVID-19.
- Section 6.2 was updated to include incidence rates for adverse events of special interest.
- Section 7.1 was updated to include approach for handling subjects that moved to Study A3921288 (Riveting) or Japan post-marketing surveillance study, or discontinued due to regulatory approval in Japan, or had dose escalation.
- Section 8.2.4 was updated to include listing of subjects with dose reduction due to pulmonary embolism (PE) risk factors and analyses for incidence rates.

Major changes from Version 1 to Version 2 include:

- Section 2 and Section 4.2.1 were updated based on the protocol Amendment 8.
- Section 5.3 was updated to add subpopulations.
- Section 7 was updated to add the non-responder imputation (NRI) for binary endpoints, and last observation carried forward (LOCF) for continuous endpoints.
- Section 8.2 was updated to include details of data summaries to be done in each subpopulation.
- Appendix 1 was updated for definition and use of visit windows.

C

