7. HANDLING OF MISSING VALUES

7.1. Efficacy Endpoints

For binary efficacy endpoints (Remission, Clinical remission, Mucosal healing, PMS remission, Clinical response) derived from Mayo subscores (site-read endoscopic subscore was used), data will be summarized based on the observed-case data and non-responder imputation and last observation carried forward imputation (NRI-LOCF). The NRI-LOCF approach is described as the following:

- For subjects who discontinued from the study, other than those who moved to Study A3921288 or to the Japan post-marketing surveillance study, or due to regulatory approval in Japan, NRI will be used for missing data up to the visit (using the lower bound of visit window as defined in [Appendix 1](#)) they would have reached if they had stayed at the study. The missing data before time of discontinuation will be imputed as non-responders.
- For ongoing subjects (for interim analyses only), they will be included in the summary tables only up to visits with non-missing data in the dataset for the interim report. For subjects with intermittent missing data, they will be treated as non-responders. Otherwise no imputation for missing data will be applied since it's hard to separate the true missing data from being late for the scheduled visit.
- For completed subjects, they will be included in the summary tables only up to the completion visit. Missing data before the completion will be imputed using the NRI approach.
- For subjects who discontinued from the study and moved to Study A3921288 or to the Japan post-marketing surveillance study, or due to regulatory approval in Japan, LOCF will be used up to the visit (using the lower bound of visit window as defined in [Appendix 1](#)) they would have reached if they had stayed in the study. The missing data before time of discontinuation will be imputed as non-responders. This approach will likely overestimate the proportions of subjects who achieve the binary endpoints since it is assumed that the response status remains after subjects moved to Study A3921288 or the Japan post-marketing surveillance study.

For continuous endpoints total Mayo score and Partial Mayo score, data will be summarized based on the observed-case data and LOCF. The LOCF approach is described as the following:

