7.2. PRO Endpoints

For the PRO endpoints based on IBDQ, CCI [REDACTED] rules suggested by the developers of the questionnaires will be followed in calculating the endpoints with any missing items. If these rules are not sufficient to impute the missing values, then the missing values will be handled as following:

- For IBDQ binary endpoints IBDQ remission and deterioration (worsening) in IBDQ bowel symptom domain, they will be handled in the same way as binary efficacy endpoints as specified in section 7.1 for missing data and data after the dose escalation.
- For IBDQ CCI [REDACTED] continuous endpoints, they will be handled in the same way as continuous efficacy endpoints as specified in section 7.1 for missing data and data after the dose escalation.

CCI [REDACTED]

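### In the NRI-LOCF tables, PMS and IBDQ remission visits missed because of COVID-19 count as non-response, and no planned table separates them from true dropouts

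*SAP*

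**What the plan says.** SAP 5.5 treats COVID-19 as a category of protocol deviation to be listed: "A full list of protocol deviations for the study report will be compiled prior to database closure including protocol deviations related to COVID-19". The Version 3 change list agrees: "Section 5.5 was updated to mention protocol deviations related to COVID-19". Its separate entry for section 7.1 names transfers to Study A3921288, the two Japan-related departures and dose escalation, but not COVID-19.

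SAP 7.1 tabulates each binary efficacy endpoint, PMS remission included, in two ways: on observed cases and under NRI-LOCF. In the NRI-LOCF version:

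- Completers: "Missing data before the completion will be imputed using the NRI approach". Their denominator ends with completion: "For completed subjects, they will be included in the summary tables only up to the completion visit".
- Subjects who discontinued: "The missing data before time of discontinuation will be imputed as non-responders". This sentence appears both for ordinary dropouts and for subjects who moved to A3921288 or left for a Japan-related reason.
- Visits due after discontinuation: NRI applies, with a short list of exceptions. The rule begins "For subjects who discontinued from the study, other than those who moved to Study A3921288 or to the Japan post-marketing surveillance study" and adds departures due to Japanese approval. Leaving because of the pandemic is not on the list.

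For IBDQ remission, once the questionnaire developers' missing-item rules are exhausted, SAP 7.2 states that "they will be handled in the same way as binary efficacy endpoints as specified in section 7.1 for missing data".

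**The concern.** A subject in stable remission whose spring 2020 visit did not take place, and who has no assessment in that analysis window, is tabulated as not in remission. A subject who left the study because of the pandemic is tabulated as not in remission at every later visit due. Neither event says anything about the drug.

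The effect is confined to late visits. Protocol Amendment 11 records that all subjects had already passed Month 36, so the full-Mayo endpoints at Months 2 to 36 are out of reach. What remains is PMS remission, assessed every three months, and IBDQ remission, assessed annually after Month 36. Amendment 10 extended the study by two years to collect more long-term safety and efficacy data, so the exposed visits are largely the ones the extension added.

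The observed-case table does not settle the matter. It leaves out pandemic gaps, but it also leaves out subjects who stopped for lack of efficacy or adverse events. One planned table counts both kinds of missing data as failure and the other drops both. Neither keeps true dropouts as failures while setting pandemic gaps aside, so the difference between the tables cannot be attributed to one cause.

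**Working it through.** **Rule check.** For an intermittent missed visit, 7.1 gives the same result for completers, ordinary dropouts and exempt movers: non-response. The reason for the gap is not consulted. The post-discontinuation exception covers only A3921288, the Japan post-marketing study and Japanese approval. The 5.5 list feeds no step in 7.1 or 7.2.

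**Mechanism.** Let r be the remission rate among subjects still on study and m the share of visits missed for COVID-19, unrelated to response. NRI gives r × (1 − m); observed-case gives r. Example with 100 visits due, r = 80% and m = 10%: NRI 72/100 = 72%, observed-case 72/90 = 80%.

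**Pull on the tabulated rate.** The NRI denominator keeps ordinary dropouts up to the visit they would have reached, so

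pull = s × m × r × a,

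where s is the share of the visit's denominator whose visit falls in the disrupted period and a is the share still on study.

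**Inputs.** From the documents: study end about July 2020, and participation from about 4 to more than 7 years. Assumed, because the documents give no figures: uniform enrolment from October 2012 to July 2016, disruption from 15 March to 31 July 2020 (138 days), m = 10–50%, r = 70%, a = 30–60%.

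**Shares.** From 1 October 2012 to 31 July 2020 is 2,860 days. Reach at Month M is 2,860 minus the days to that visit, using calendar months (30.44 days) or the target days in SAP Appendix 1.

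- Month 72: 138/700 = 0.20 (Day 2160) or 138/668 = 0.21 (calendar).
- Month 84: 138/340 = 0.41 (Day 2520) or 138/303 = 0.455 (calendar).
- Month 48: everyone enrolled has reached it, so the share depends on when in July 2016 enrolment closes. In calendar months it is 108/1,369 = 0.08 (1 July) or 138/1,399 = 0.10 (31 July).

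| Visit | s | Low: s × 0.10 × 0.70 × 0.30 | High: s × 0.50 × 0.70 × 0.60 |
|---|---|---|---|
| Month 48 | 0.08–0.10 | 0.2 points | 2.1 points |
| Month 72 | 0.20–0.21 | 0.4 points | 4.4 points |
| Month 84 | 0.41–0.455 | 0.9 points | 9.6 points |

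**Cross-check with different assumptions.** Take five pandemic months, maximum follow-up of 90 months, r = 80%, m = 10–30% and a = 30–60%, so that s = 5/(90 − M). The pull is 0.3–1.7 points at Month 48 (s = 0.12), 0.7–4.0 at Month 72 (s = 0.28) and 1.0–6.0 at Month 78 (s = 0.42). Direction, order of size and growth with visit month agree.

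**Windows.** Late analysis windows are 90 days wide (Month 60: Days 1756–1845), against a protocol visit window of ±7 days, so a delay of up to about 45 days past target still yields an observed value. The last window is open-ended (Day 2476 onward), so a later visit can fill a missed Month 84. The figures above are therefore upper estimates, most of all at Month 84. For IBDQ the windows help less: Appendix 1 moves an off-schedule assessment to the next scheduled window. A Month 48 questionnaire completed after Day 1485 would go to Month 60 and leave Month 48 as non-response.

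**The case against.** The strongest reply is that NRI is a uniform, conservative convention and that the SAP already plans an observed-case table beside it. Safety is the primary analysis and is observed-case without imputation (SAP 7.3), no hypothesis is tested, and only two descriptive secondary endpoints are touched. All of this stands, and it sets the priority. It does not supply a table that isolates the pandemic gaps.

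Three stronger readings are tempting, and the documents do not support them.

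- A reader might infer that the late remission rates in general are pulled down. Only the NRI-LOCF summary is.
- A reader might infer that the SAP contradicts itself by exempting other administrative gaps. It does not do so for missed visits: the subjects exempted after discontinuation still have earlier gaps imputed as non-response. The comparison is fair only for subjects who discontinued because of the pandemic.
- A reader might infer that the NRI-LOCF rates are too low on balance. SAP 7.1 itself warns that carrying forward the last status of transferred subjects will probably overstate response in the same tables, so the net direction is not known.

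It is also fair to object that a pull calculated among on-study subjects alone overstates the effect. The same inputs would give about 1.4 to 7 points at Month 72 and 2.9 to 16 at Month 84, but dropouts stay in the NRI denominator, so the smaller figures apply.

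Finally, part of section 7.1 is blacked out, so a COVID-19 rule there cannot be wholly excluded. The Version 3 change list points to none.

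**Conclusion.** The point holds for the NRI-LOCF summary of PMS and IBDQ remission after Month 36, and no further. Following the stated rule, visits lost to COVID-19 with no data in the window become non-response. Discontinuation because of the pandemic becomes non-response at every later visit due.

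The size is small to moderate and increases with visit month, as tabulated above. The enrolment pattern, disruption dates, miss rate, response rate and retention behind it are all assumptions. It covers missed visits only, since the documents give no basis for a number of pandemic discontinuations, and it shrinks wherever a rescheduled visit falls inside the window. This is a minor point: no test, no primary endpoint and no safety result depends on it.

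**What to change.** Add a rule to SAP 7.1, carried into 7.2. Where a visit has no assessment in its analysis window and a COVID-19 reason is recorded, leave the subject out of both numerator and denominator at that visit. Visits with data in the window stay in, even if they appear on the deviation list as late or partial. State explicitly whether visits due after a discontinuation with a recorded COVID-19 reason fall under the same rule. Report the number of subjects affected at each visit, and keep the NRI-LOCF table as now specified alongside as a sensitivity analysis. Settle this before database release.

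The cost is a sentence or two in the SAP, a flag derived from the deviation list already planned, and one further tabulation. The downsides are slightly smaller denominators at late visits and an assumption that COVID-19 missingness is unrelated to response. Keeping the existing NRI-LOCF table beside the new one shows how much rests on that assumption.

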6. ENDPOINTS AND COVARIATES

Measurement will be collected/derived at visits specified in the protocol. The details of visit windows are defined in [Appendix 1](#). Unless specifically stated otherwise, the baseline value is defined as the last non-missing measurement collected prior to the first administration of study medication in this study, A3921139, at Day 1.

6.1. Efficacy Endpoints

Efficacy endpoints will be based upon the Mayo score and partial Mayo score. The Mayo score is an instrument designed to measure disease activity of ulcerative colitis. Mayo score ranges from 0 to 12 points. It consists of 4 subscores, each graded from 0 to 3 with higher scores indicating more severe disease.

- Stool frequency (0-3);
- Rectal bleeding (0-3);
- Findings of flexible sigmoidoscopy (0-3);
- Physician global assessment (PGA) (0-3).

A partial Mayo score (PMS) is an instrument designed to measure disease activity of UC without endoscopy. Partial Mayo score ranges from 0 to 9 points.

An endoscopy will be performed at Baseline, Month 2, at annual study visits (Months 12, 24 and 36), and at the early withdrawal/early termination visit. The endoscopic subscores at all applicable visits will be read by study site investigator. However, at Month 2 visit, the endoscopic score will be read by both central reader and site investigators prior to Amendment 8. After implementation of Amendment 8, the Month 2 endoscopic subscore will be read by study site investigator only. The endpoints that require the endoscopic subscore component will be derived based on local-read endoscopic subscores, as well as central-read endoscopic subscores, if available.

Further information on the Mayo score is given in [Appendix 2.1](#).

6.1.1. Primary Endpoint

As this is an open-label extension study, there is no primary efficacy endpoint.

6.1.2. Secondary Endpoints

- Remission. Remission in this study is defined as a Mayo score ≤ 2 with no individual subscore > 1 , and rectal bleeding subscore of 0.
- Clinical remission. Clinical remission in this study is defined as a Mayo score ≤ 2 with no individual subscore > 1 .
- Partial Mayo score (PMS) remission. PMS remission in this study is defined as a partial Mayo score ≤ 2 with no individual subscore > 1 .
- Mucosal healing. Mucosal healing is defined as a Mayo endoscopic subscore of 0 or 1.

CCI [REDACTED]

[REDACTED]

[REDACTED]

[REDACTED]

[REDACTED]

6.2. Safety Endpoints

- Incidence and severity of adverse events.
- Incidence of serious infections.
- Incidence and severity of clinical laboratory abnormalities, and change from baseline in clinical laboratory values.
- Incidence of vital sign abnormalities and change from baseline in vital signs.
- Incidence of clinically significant changes in physical examinations from baseline.
- Incidence of electrocardiogram (ECG) abnormalities during treatment.
- Summary of adjudicated safety events (eg, cardiovascular, malignancy, opportunistic infections, hepatic events).

- Proportion of subjects with addition of lipid lowering agents.
- Proportion of subjects whose dose is decreased to 5 mg BID from 10 mg BID.

CCI
I [Redacted]

6.3. Other Endpoints

6.3.1. Patient Reported Outcome (PRO) Endpoints

Section 7.2 of the protocol gives details on the IBDQ, CCI [Redacted]

- IBDQ remission, defined as total score in Inflammatory Bowel Disease Questionnaire (IBDQ) ≥ 170 over time.
- The scores and change from Baseline (of Study A3921139) in total IBDQ score and domains (Bowel Symptoms, Systemic Symptoms, Emotional Function and Social Function) over time.

CCI
I [Redacted]

I [Redacted]

I [Redacted]

I [Redacted]

I [Redacted]

I [Redacted]

6.4. Covariates

- None.

7. HANDLING OF MISSING VALUES

7.1. Efficacy Endpoints

For binary efficacy endpoints (Remission, Clinical remission, Mucosal healing, PMS remission, Clinical response) derived from Mayo subscores (site-read endoscopic subscore was used), data will be summarized based on the observed-case data and non-responder imputation and last observation carried forward imputation (NRI-LOCF). The NRI-LOCF approach is described as the following:

- For subjects who discontinued from the study, other than those who moved to Study A3921288 or to the Japan post-marketing surveillance study, or due to regulatory approval in Japan, NRI will be used for missing data up to the visit (using the lower bound of visit window as defined in [Appendix 1](#)) they would have reached if they had stayed at the study. The missing data before time of discontinuation will be imputed as non-responders.
- For ongoing subjects (for interim analyses only), they will be included in the summary tables only up to visits with non-missing data in the dataset for the interim report. For subjects with intermittent missing data, they will be treated as non-responders. Otherwise no imputation for missing data will be applied since it's hard to separate the true missing data from being late for the scheduled visit.
- For completed subjects, they will be included in the summary tables only up to the completion visit. Missing data before the completion will be imputed using the NRI approach.
- For subjects who discontinued from the study and moved to Study A3921288 or to the Japan post-marketing surveillance study, or due to regulatory approval in Japan, LOCF will be used up to the visit (using the lower bound of visit window as defined in [Appendix 1](#)) they would have reached if they had stayed in the study. The missing data before time of discontinuation will be imputed as non-responders. This approach will likely overestimate the proportions of subjects who achieve the binary endpoints since it is assumed that the response status remains after subjects moved to Study A3921288 or the Japan post-marketing surveillance study.

For continuous endpoints total Mayo score and Partial Mayo score, data will be summarized based on the observed-case data and LOCF. The LOCF approach is described as the following:

- For subjects who discontinued from the study, other than moved to Study A3921288 or to the Japan post-marketing surveillance study, or due to regulatory approval in Japan, LOCF approach will be used for missing data up to the visit (using the lower bound of visit window as defined in [Appendix 1](#)) they would have reached if they had stayed in the study. Any missing data before time of discontinuation will be imputed using LOCF.

- For ongoing subjects (for interim analyses only), they will be included in the summary tables only up to visits that are included in the dataset for the interim report. For intermittent missing data, LOCF approach will be applied. Otherwise no imputation for missing data will be applied since it's hard to separate the true missing data from being late for the scheduled visit.
- For completed subjects, they will be included in the summary tables only up to the completion visit. Missing data before the completion will be imputed using LOCF approach.
- For subjects who discontinued from the study and moved to Study A3921288 or to the Japan post-marketing surveillance study, or due to regulatory approval in Japan, LOCF approach will be used after the time of discontinuation up to the visit (using the lower bound of visit window as defined in [Appendix 1](#)) they would have reached if they had stayed in the study. Any missing data before time of discontinuation will be imputed using LOCF.

To implement LOCF, individual components were carried forward first, then the endpoints were derived using the imputed components.

The central read endoscopic subscore was only assessed at baseline and Month 2 visit for subjects who enrolled prior to protocol Amendment 8. For subpopulations other than induction non-responder subpopulation, the endpoints using central-read endoscopic subscore as a component will be summarized based on observed data only. No NRI or LOCF imputation will be applied. However, for induction non-responder subpopulation, subjects were expected to complete Month 2 visit prior to implementation of protocol Amendment 8, endpoints using central-read endoscopic subscore as a component will be summarized based on both NRI for binary endpoints (or LOCF for continuous endpoints), and observed data for Month 2.

CCI [REDACTED]

[REDACTED]

[REDACTED]

[REDACTED]

[REDACTED]

CCI
I

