- Be in stable remission on tofacitinib 10 mg BID for the 6 month period in Study A3921139 up to and including the baseline visit of Study A3921288, defined as meeting all the following criteria:
 - A partial Mayo score ≤ 2 , with no individual subscore > 1 and a rectal bleeding subscore of 0 at each study visit during the 6 month period in Study A3921139 prior to and at baseline of Study A3921288; AND
 - At least one assessment of remission based on Mayo score.
- Not be receiving any corticosteroids to treat their UC for at least 4 weeks prior to the baseline visit of Study A3921288.

[figure not shown]
Study A3921288 will evaluate the efficacy and safety of tofacitinib in subjects in stable remission on 10 mg BID who decrease the dose to and remain on 5 mg BID compared to subjects who remain on 10 mg BID.

All subjects who withdraw early or who complete this open-label study, with the exception of those subjects entering Study A3921288, will have a 4-week safety follow-up evaluation after the last dose of study medication.

Subjects will be required to remain on stable doses of their concomitant medications for UC during the study period. Subjects who enter this study on corticosteroids (eg, subjects who withdraw from Study A3921096 due to treatment failure or non-responders at the end of Study A3921094 or A3921095) will need to continue the steroid tapering regimen described in Study A3921096. If a subject requires rescue therapy or undergoes surgery, the subject should be withdrawn from the study and appropriate agents should be given at the discretion of the investigator.

Per protocol Amendment 11, Version 18 June 2019, the study investigator or designee will be required to ask each subject at each study visit if he/she has any newly-developed risk factors for PE, and if one is identified, the subject will need to have their tofacitinib dose adjusted to 5 mg BID if they are taking open label 10 mg BID.

Figure 1. Study Design

- Study visits will occur every 3 months after the first year until approximately July 2020.
- All subjects will have a 4-week follow-up evaluation after their last dose of study medication.

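### NRI-LOCF carries A3921288 transfers forward as responders, which by the SAP's own account likely overestimates late remission rates, and no readable summary bounds this from below

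*SAP*

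**What the plan says.** SAP 7.1 names two summaries for the binary efficacy endpoints: observed-case and NRI-LOCF. Within NRI-LOCF the rule depends on why a subject left.

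- Ordinary discontinuations: "NRI will be used for missing data up to the visit" the subject would have reached.
- Leavers to A3921288 or the Japan post-marketing study, or because of regulatory approval in Japan: "LOCF will be used up to the visit" they would have reached.
- Completers: "they will be included in the summary tables only up to the completion visit".

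Data missing before exit count as non-response in all three groups. On the carry-forward the SAP concedes: "This approach will likely overestimate the proportions of subjects who achieve the binary endpoints". Its reason is "since it is assumed that the response status remains after subjects moved to Study A3921288 or the Japan post-marketing surveillance study". It adds: "To implement LOCF, individual components were carried forward first, then the endpoints were derived using the imputed components". SAP 7.2 applies the same rules to IBDQ remission.

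SAP 2.1 sets the entry conditions for A3921288: at least two consecutive years on 10 mg BID in this study; six months with partial Mayo score at most 2, no subscore above 1 and no rectal bleeding at each visit; and at least one Mayo-based remission. That study evaluates "subjects in stable remission on 10 mg BID who decrease the dose to and remain on 5 mg BID" against those who stay on 10 mg BID.

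**The concern.** The six-month entry condition is stricter than the PMS remission definition in SAP 6.1.2. An eligible A3921288 transfer is therefore a PMS responder at exit, and the carry-forward keeps that status. The same will usually hold for Mayo-based remission. It is likely but not guaranteed for IBDQ remission, since entry sets no IBDQ threshold.

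The rule assumes that response persists in full, yet A3921288 asks what happens when some of these subjects reduce their dose. By default SAP 8.2.3 groups subjects by initial dose assignment in A3921139, so a transfer who reduces in A3921288 would still count as a responder under the initial assignment.

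The stake is how to read the late efficacy rates, which serve the secondary objectives of long-term efficacy and quality of life. The SAP gives the likely direction of the bias but, in the readable text, nothing that shows its size or a figure below it.

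**Working it through.** **Inputs.** The plan states no number of leavers, no remission rate and no size for the overestimate, so there is no figure to reproduce. The one related number is the planned size, 460 + 440 = 900 (SAP 4.2.1). All other inputs below are assumptions.

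**Notation at one visit.** N subjects are due: O observed, of whom r respond; D ordinary discontinuations; M leavers under the carry-forward rule, of whom a share q carry responder status. A fraction s of the carried responders truly stay in response.

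- Observed-case = r/O
- NRI-LOCF = (r + qM)/N
- Leavers as non-responders = r/N
- Leavers included only up to exit = r/(N − M)

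**Is either planned summary a lower bound for the leavers?** Since O ≤ N, r/O ≥ r/N. Since qM ≥ 0, (r + qM)/N ≥ r/N. Both planned figures are always at or above r/N, so neither is a guaranteed lower bound.

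**Size of the carry-forward overstatement.** It is (qM/N) × (1 − s). With N = 900 and q = 1, in percentage points:

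| Transfers M | s = 90% | s = 75% | s = 60% |
|---|---|---|---|
| 50 | 0.6 | 1.4 | 2.2 |
| 100 | 1.1 | 2.8 | 4.4 |
| 150 | 1.7 | 4.2 | 6.7 |

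For example, 150/900 × 0.40 = 6.7 points. Efficacy is also reported by subpopulation, where the share can be larger. With 50 transfers among the roughly 440 subjects expected from induction, the range is 50/440 × 0.10 = 1.1 to 50/440 × 0.40 = 4.5 points.

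**What the tables would show.** Take 100 transfers, all carried as responders, and 250 responders among the other 800.

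- NRI-LOCF: 350/900 = 38.9%
- Leavers up to exit only: 250/800 = 31.3%
- Leavers as non-responders: 250/900 = 27.8%
- If 75% of transfers truly persist: 325/900 = 36.1%

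**Net direction against the truth.** Per 100 subjects due:

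- D = 40, M = 10, O = 50, observed rate 60% (r = 30), q = 1, s = 0.8, and 20% of ordinary dropouts truly in remission. NRI-LOCF is 30 + 10 = 40%; the truth is 30 + 8 + 8 = 46%. NRI-LOCF is too low.
- D = 5, M = 30, O = 65, observed rate 40% (r = 26), q = 1, s = 0.8, and no ordinary dropout in remission. Observed-case is 40%; the truth is 26 + 24 = 50%. Observed-case is too low.

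**Which visits are exposed.** The two-year condition puts A3921288 exits at about Month 24 or later. Full Mayo scores are scheduled at Months 2, 12, 24 and 36 (Protocol 7.1.3), so A3921288 exits can affect remission, clinical remission and mucosal healing essentially only at Month 36. PMS and IBDQ continue after Month 36 (Schedule of Activities), so the effect can accumulate there. No minimum time is stated for the Japan exits.

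**The case against.** The strongest reply is that the rule is reasoned and disclosed. Transfers leave because they are doing well, so counting them as failures would be harsh. In the example, NRI-LOCF at 75% retention misses by 38.9 − 36.1 = 2.8 points, against 36.1 − 31.3 = 4.9 for the exit-visit table (from unrounded figures) and 36.1 − 27.8 = 8.3 for non-response. NRI-LOCF is closest whenever retention exceeds about 66%, since the midpoint of 31.25% and 38.9% is about 35.1%, or some 316 of 900, which is 66 of the 100 transfers. This stands, and it is why NRI-LOCF should be kept and the non-response table presented as a bound only.

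Four stronger readings are tempting, and the documents do not support them.

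- *Every such leaver becomes a permanent responder.* No remission condition is stated for the Japan exits. LOCF carries the last components, so a Japan leaver not in remission is carried as a non-responder, and the carry-forward ends at the visit the subject would have reached.
- *Both planned summaries err upward.* Observed-case drops failures, but it also drops the transferring successes. NRI-LOCF counts ordinary dropouts and missed visits as non-response. The two cases above show each falling below the truth.
- *Handling completers differently is an inconsistency.* Completers leave because follow-up ends; transfers leave because they are in remission. Dropping transfers at exit removes successes selectively, so that table is a sensitivity view and not a correction.
- *The SAP contains no bounding analysis at all.* Part of 7.1 is redacted. SAP 7.2 refers to 7.1 for data after dose escalation, and no such rule is readable there, so some missing-data text evidently sits under the redaction. The statement can be made only of the readable text.

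The stakes are also limited: the primary objective is safety, there is no primary efficacy endpoint and no hypothesis is tested.

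**Conclusion.** The point holds in a limited form. For A3921288 transfers, NRI-LOCF fixes PMS response by construction, and usually Mayo-based response, at every later visit they would have reached. The SAP concedes that this likely overestimates the rates, and no readable summary gives a figure below it. The carry-forward component is about 0.6 to 6.7 percentage points under the assumptions in the table (50 to 150 transfers, 60 to 90% retention, all carried as responders, N = 900). The true size cannot be computed from the documents.

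A reader might infer that the reported long-term remission rates are overstated overall. That does not follow: only the carry-forward component has a known direction, and the net bias may go either way. This is a cheap improvement to the plan, not an error that invalidates it.

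**What to change.** Keep NRI-LOCF. In SAP 7.1, for each binary endpoint (and through 7.2 for IBDQ remission), add:

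1. A sensitivity table that counts subjects leaving for A3921288, the Japan post-marketing study or Japan approval as non-responders after exit. Label it a lower bound for the leavers, not a best estimate.
2. Optionally, a table that includes them only up to the exit visit.
3. The number and last status of carried-forward leavers, by destination and visit.

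Quote the resulting range beside the NRI-LOCF figure. If the redacted part of 7.1 already holds such an analysis, a statement to that effect closes the first item.

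The cost is a few lines of SAP wording, two extra runs of existing tables and a count table, all from data already held. The downside is that a less favourable lower figure is shown.
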